- mPFS-1: Historically, the mPFS for previously treated mCRC patients treated with RGF is 1.9 mos. We predict VOR/HCQ will improve mPFS to 3.8 months. We expect 5% lost to follow-up. Assuming a 36-month accrual period with 1 year for follow up, 36 subjects per group are necessary to obtain 80% power. With 5% lost to follow-up the sample size required per group is 38 ($=36/0.95$), therefore, the total required sample size is 76 subjects. As a result, the target accrual rate is 2-4 patients/month to achieve a target accrual at 36 months with an additional 12-month follow-up.

Interim analysis: The O'Brien-Fleming procedure will be used to conduct an interim analyses for efficacy when 50% of the patients complete the study. A statistical basis for stopping the study at the first look will be achieved if the test statistic indicates benefit in the VOR/HCQ Arm and exceeds 2.96259, corresponding to a significance level of 0.003. If the test statistic does not exceed 2.96259 at the first look then the trial will proceed to the final analysis. A treatment effect will be declared significant and beneficial at the final analysis if the test statistic indicates benefit and exceeds 1.96857, corresponding to a significance level of 0.047. If a treatment effect is not declared at the interim analysis, a statistical basis for stopping the study for futility will be attained if the conditional power is less than or equal to 20%.

Analytic plan for secondary objectives:

- OS: The analyses of median OS will be performed in the intent-to-treat population. OS will be illustrated with Kaplan-Meier plots, the estimate of median OS with its 95% confidence interval.
- mPFS-2: The analyses of median PFS-2 will be performed in the crossover population (crossover is optional). mPFS-2 will be illustrated with Kaplan-Meier plots, the estimate of median PFS-2 with its 95% confidence interval. Treatment groups will be contrasted with regard to the response rate with a logistic regression model adjusted for age, sex, race and the baseline tumor K-RAS status (mutated, wild type); the odds ratio, its 95% confidence interval, and the p-value for testing the null hypothesis that the log odds ratio is zero will be presented. If the logistic model fails due to small cell counts then treatments will be contrasted with regard to response using Fisher's Exact Test.

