3.0 Statement of Study Objectives

Primary Objective:

- To determine the clinical efficacy with progression-free survival (PFS-1) of the combination of VOR plus HCQ when compared to RGF in treatment-refractory mCRC.

Secondary Objectives:

- To determine the overall survival in refractory mCRC patients receiving VOR plus HCQ when compared to RGF.
- To determine the progression-free survival (PFS-2) of the crossover treatment (crossover is optional).
- To evaluate the tumor response rate in refractory mCRC patients receiving VOR plus HCQ when compared to RGF.
- To further define the safety of the combination of VOR/HCQ when compared to RGF in treatment-refractory mCRC.
- To identify biomarkers of autophagy and anti-angiogenic inhibition that are associated with clinical efficacy of VOR/HCQ and RGF, respectively, in mCRC.

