7.0 Data Collection

Data will be entered into Case Report Forms (CRF), which are currently in paper form.

For each patient on study, the following will be documented:

- Lab values: CBC, CMP, CEA, PTT/INR (when collected)
- PFS-1: measured from the start of the first treatment the patient is randomized to until the date the criteria for progression are met or the date the patient is taken off study for any reason, whichever is shorter).
- OS: measured from the start of treatment on trial until the death of the patient (date of death)
- PFS-2: measured from the start of the crossover treatment (Optional, second regimen) until the date the criteria for progression are met or the date the patient is taken off study for any reason, whichever is shorter.
- Response: measured as best response at any given time: complete response (CR) or partial response (PR), as defined by Response Evaluation Criteria in Solid Tumors (RECIST 1.1) Committee (73). (See Appendix 13.1 for definitions of response).
- Adverse events: the number and grade 1-5 of all adverse events will be documented according to the National Cancer Institute Common Terminology Criteria for Adverse Events (NCI-CTCAE) v4.0; measured at baseline, each cycle, and at off study date.

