10.0 Statistical Section

Analytic plan for primary objective:

mPFS-1: Historically, the mPFS for previously treated mCRC patients treated with RGF is 1.9 mos. We predict VOR/HCQ will improve mPFS to 3.8 months. We expect 5% lost to followup. Assuming a 36-month accrual period with 1 year for follow up, 36 subjects per group are necessary to obtain 80% power. With 5% lost to follow-up the sample size required per group is 38 ($=36/0.95$), therefore, the total required sample size is 76 subjects. As a result, the target accrual rate is 3-4 patients/month to achieve a target accrual at 36 months with an additional 12month follow-up.

Treatments will be contrasted with regard to PFS-1 with a proportional hazards model with adjustment for age, sex, race, and the baseline tumor K-RAS status (mutated, wild type); the adjusted hazard ratio, its 95% confidence interval, and the p-value for testing the null hypothesis that the log hazard ratio is zero will be presented. Survival curves will be illustrated with Kaplan-Meier plots. Interactions between treatment and baseline covariates will be explored.

If a patient does not complete Cycle 1 and is off study, then this patient will not be evaluable for efficacy but will be evaluable for toxicity.

Interim analysis: The O'Brien-Fleming procedure will be used to conduct an interim analyses for efficacy when 50% of the patients complete the study. A statistical basis for stopping the study at the first look will be achieved if the test statistic indicates benefit in the VOR/HCQ Arm and exceeds 2.96259, corresponding to a significance level of 0.003. If the test statistic does not exceed 2.96259 at the first look then the trial will proceed to the final analysis. A treatment effect will be declared significant and beneficial at the final analysis if the test statistic indicates benefit and exceeds 1.96857, corresponding to a significance level of 0.047. If a treatment effect is not declared at the interim analysis, a statistical basis for stopping the study for futility will be attained if the conditional power is less than or equal to 20%.

Analytic plan for secondary objectives:

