- OS: The analyses of median OS will be performed in the intent-to-treat population. OS will be illustrated with Kaplan-Meier plots, the estimate of median OS with its 95% confidence interval. Treatment groups will be contrasted with regard to the response rate with a logistic regression model adjusted for age, sex, race and the baseline tumor K-RAS status (mutated, wild type); the odds ratio, its 95% confidence interval, and the p-value for testing the null hypothesis that the log odds ratio is zero will be presented. If the logistic model fails due to small cell counts then treatments will be contrasted with regard to response using Fisher's Exact Test.
- mPFS-2: The analyses of median PFS-2 will be performed in the crossover population. Crossover to the other arm will be allowed, but OPTIONAL, and will be determined by the treating physician for the patient's best interest. mPFS-2 will be illustrated with KaplanMeier plots, the estimate of median PFS-2 with its 95% confidence interval. Treatment groups will be contrasted with regard to the response rate with a logistic regression model adjusted for age, sex, race and the baseline tumor K-RAS status (mutated, wild type); the odds ratio, its 95% confidence interval, and the p-value for testing the null hypothesis that the log odds ratio is zero will be presented. If the logistic model fails due to small cell counts then treatments will be contrasted with regard to response using Fisher's Exact Test.
- Response rates: Response rates will be measured as the proportion of patients with the best response, complete response (CR) or partial response (PR), as defined by RECIST 1.1 Criteria and a 95% confidence interval. (See Appendix 13.2 for RECIST 1.1 criteria)
- Adverse events: All adverse events will be listed by type and grade. All adverse events will be listed by treatment group, level of seriousness (serious, not serious). Treatments will be contrasted with regard to each adverse event with Fisher's Exact Test.

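### Overall survival has a comparative objective but no between-arm estimate or test, and the response comparison is placed under OS and PFS-2 instead of under response rates

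*Combined protocol and SAP*

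**What the plan says.** - **Objectives (Section 3.0, repeated in the Synopsis).** OS is a comparative secondary objective: "To determine the overall survival in refractory mCRC patients receiving VOR plus HCQ when compared to RGF". Tumour response is worded as a comparison with regorafenib (RGF) too.
- **OS analysis (Section 10.0 and Synopsis).** The population is set by "OS: The analyses of median OS will be performed in the intent-to-treat population", and the output is "OS will be illustrated with Kaplan-Meier plots, the estimate of median OS with its 95% confidence interval". The Synopsis bullet stops there. The Section 10.0 bullet goes straight on to "Treatment groups will be contrasted with regard to the response rate with a logistic regression model adjusted for age, sex, race", with Fisher's exact test as the fallback.
- **PFS-2 bullet (Section 10.0 and Synopsis).** The same logistic/Fisher text on response appears here, in a bullet whose population is the patients who crossed over.
- **Response-rates bullet.** "Response rates will be measured as the proportion of patients with the best response", with a 95% confidence interval. No contrast is given.
- **PFS-1.** "Treatments will be contrasted with regard to PFS-1 with a proportional hazards model with adjustment for age, sex, race" and K-RAS status, with hazard ratio, interval and p-value.
- **OS definition (Synopsis, Sections 5.7 and 7.0).** The clock runs from the start of trial treatment to death.
- **Evaluability (Section 10.0, under the primary objective).** "If a patient does not complete Cycle 1 and is off study, then this patient will not be evaluable for efficacy".

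**The concern.** A comparative objective needs a stated measure of the difference between arms. Two Kaplan-Meier curves and two medians describe each arm but do not estimate that difference. Other secondary endpoints do get a named between-arm analysis in Section 10.0: logistic regression or Fisher's test for response, and Fisher's test for adverse events. OS is the exception.

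If nothing changes, the model, population, time origin, censoring rule and reading of the OS comparison under optional crossover will be settled after the data are seen. The response comparison has a related problem. The bullets that carry it name either the intent-to-treat or the crossover population, and Section 7.0 records response as "Response: measured as best response at any given time". It is therefore unclear whose response, and on which treatment, is compared.

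**Working it through.** **1. The plan's own figure.** The only sample size is for PFS-1. With medians of 1.9 and 3.8 months the hazard ratio (HR) is 0.50. Freedman's formula (two-sided 0.05 assumed, 80% power) gives 71 events. The average event probability over 36 months' accrual plus 12 months is 0.991, so 71 / 0.991 / 2 = 35.8, or 36 per group. Then 36 / 0.95 = 37.9, or 38 per group and 76 in total. The stated figures reproduce. No events, power or alpha are stated for OS.

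**2. Where the contrasts sit.**

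| Endpoint | Objective comparative? | Contrast in its own bullet, Section 10.0 | Synopsis |
|---|---|---|---|
| PFS-1 | Yes | Adjusted proportional hazards | Interim and final test thresholds; no model named |
| OS | Yes | On response only | None |
| PFS-2 | No | On response only | On response only |
| Response | Yes | None | None |

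Sections 5.7 and 7.0 add no OS contrast. The biomarker proportional hazards models also use PFS-1.

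**3. Population against time origin.** Intent-to-treat means all randomised patients, but a clock that starts at first dose is undefined for anyone who never takes one. It also leaves out the wait between randomisation and first dose.

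**4. What an OS comparison could deliver.** Assumptions: exponential survival; median 6.4 months (the RGF figure in Section 2.2.1); no crossover effect; two-sided 0.05; 72 (2 × 36) to 76 patients; 12 months of follow-up each, as the Synopsis and Section 5.3.1 state.

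- *Deaths under equal survival* = N × (1 − 0.5^(12/6.4)) = N × 0.7274. This is 52.4 for N = 72 and 55.3 for N = 76.
- *95% CI factor* = exp(1.96 × 2/√deaths) = 1.72 and 1.69. Around HR 1.0 the interval runs from about 0.58 to 1.72 with 72 patients, or 0.59 to 1.69 with 76.
- *Power* (Schoenfeld) = Φ(|ln HR| × √d / 2 − 1.96), with d counted under the alternative. At HR 0.6 the second median is 10.67 months and its event probability is 1 − 0.5^(12/10.67) = 0.5415. So d = 36 × (0.7274 + 0.5415) = 45.7 and power is 41%. With 38 per arm, d = 48.2 and power is 43%.
- By the same steps, power is 23 to 24% at HR 0.7 and 12% at HR 0.8.
- *HR for 80% power*, solved with deaths under that same HR: 0.42 (41.3 deaths, N = 72) to 0.43 (43.9 deaths, N = 76).

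**5. Sensitivity.**

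- If deaths are collected to study end (uniform 36-month accrual plus 12 months), deaths = N × [1 − (e^(−12L) − e^(−48L))/(36L)] with L = ln 2/6.4, or N × 0.9315. That is 67 to 71 deaths, a CI factor of 1.61 to 1.59, and 80% power at HR 0.49 to 0.50.
- If the median is 5.0 or 10 months (12 months each, N = 72), deaths are 58 or 41 and the factor is 1.67 or 1.85.

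**The case against.** The strongest reply is that an analyst would simply apply the PFS-1 model to OS, that curves and medians are enough for an underpowered secondary endpoint, and that the response text is obviously a pasting slip. Much of this is fair. OS is underpowered, the primary analysis is untouched, and the PFS-1 model is the natural choice. But the plan does not say so, and population, origin, censoring and crossover would still be open.

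Several stronger readings are tempting, and the documents do not support them:

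- *OS is to be analysed by logistic regression.* No. The text names the response rate as its outcome. That it belongs under response rates is an inference, though a strong one.
- *The Cycle 1 rule removes early leavers from OS.* The sentence sits under the primary objective, and the OS bullet names its own population. Because it says efficacy without limit, its reach to OS is ambiguous, but this is not an outright contradiction. Nor do the documents give a usable count of such patients. The phase I figure of three rapid deteriorations among 31 enrolled comes from mixed tumours on 21-day cycles and is not the same event.
- *The late clock biases OS between arms by up to 14 days.* Section 5.2 expects both arms to start within 14 days of randomisation. RGF comes through a specialty pharmacy and later receipt is provided for, but no dispensing time is given for vorinostat plus hydroxychloroquine. The difference between arms in that wait is unknown.
- *Section 7.0 means response is pooled across both treatments.* Its wording can equally mean the best result across scans, so it needs clarifying and no more.

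**Conclusion.** The point holds as a gap in a secondary analysis that should be closed. As written, the plan produces no OS effect estimate for a comparative objective. It attaches the response contrast to OS and to the optional-crossover subset (in the Synopsis, only to the latter), and it pairs an intent-to-treat label with a clock that not every randomised patient has.

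The size is modest. Under the assumptions in the working (exponential survival, 6.4-month median, no crossover effect, 12 months each), there would be about 52 to 55 deaths under equal survival. The CI factor is 1.69 to 1.72, and power is 41 to 43%, 23 to 24% and 12% at HR 0.6, 0.7 and 0.8. Follow-up to study end improves this only to a factor of about 1.6. Either way OS is for estimation, and a non-significant result would say little. The missing contrast itself rests on the text alone and does not depend on these figures.

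**What to change.** 1. **OS bullets, Synopsis and Section 10.0.** Proposed wording: *OS runs from randomisation to death from any cause and is analysed in all randomised patients as assigned, with the PFS-1 proportional hazards model (age, sex, race, K-RAS). The hazard ratio and 95% CI are reported as estimation, with Kaplan-Meier curves and medians by arm. Patients alive or lost are censored at the date last known alive. Because crossover is optional, the hazard ratio compares treatment sequences that start with each assigned arm.* Align the OS definition in the Synopsis and Sections 5.7 and 7.0.
2. **Response.** Move the logistic/Fisher text to the response-rates bullet, applied to response on the first assigned treatment. Delete it from the OS and PFS-2 bullets, and align Section 7.0.
3. **Evaluability.** State that the Cycle 1 sentence does not apply to intent-to-treat OS.
4. **Follow-up.** Add vital-status contact to the Section 6.0 calendar. The calendar ends at the off-treatment visit, and patients who do not cross over leave the study, yet one year of follow-up per patient is already promised.

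**Cost.** These are text edits, one more secondary estimate, and the contact needed to deliver the stated follow-up. OS and PFS-1 would have different time origins, which reports must state. The primary analysis and sample size are unchanged.

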***Estimated Target Accrual (Total)**

This section asks for a **projection** of the total ethnic/racial and gender mix of the subjects

Breakdown of subjects - Indicate the total targeted/planned accrual by Race & Gender		
Race	% Male	% Female
Black or African American	3	3
American Indian or Alaskan Native		
Asian	2	2
Native Hawaiian or Other Pacific Islander		

White	45	45
More Than One Race (Multiracial)		
Total	50	50

Breakdown of subjects - Indicate the total targeted/planned accrual by Ethnicity & Gender.

Ethnicity	% Male	% Female
Hispanic or Latino	25	25
Not Hispanic or Latino	25	25
Total	50	50

Section 2: Clinical Investigator Tools for Recruitment of Minorities

Tool included in study	LIST OF TOOLS AND ACTIONS FOR INCREASING MINORITY ACCRUAL TO CLINICAL TRIALS For assistance with submitting IRB documents, developing materials in English and Spanish, and scheduling public service announcements, please contact [contact]
Yes  No 	1. Include Clinical Trial information on UT Health Cancer Center website in both English and Spanish (Please notify [contact]).
Yes  No 	2. Use of Bilingual Research Team Member or Translation services
Yes  No 	3. Identification of bilingual Patient Navigator representative of the Target Population Please specify:
Yes  No 	4. Informed Consent available in Spanish
Yes  No 	6. Information Brochures in English and Spanish** (IRB approval required)
Yes  No 	7. Flyers in English and Spanish (two sided, printed in English on one side and Spanish on the other).** (IRB approval required)
Yes  No 	8. Public Service Announcements (PSAs) or Advertisements- Spanish Radio** (IRB approval required)
Yes  No 	9. PSA's or Advertisements -Spanish newspapers (e.g., La Prensa)** (IRB approval required)
Yes  No 	10. PSA's or Advertisements -Spanish Television (e.g., Univision)** (IRB approval required)

Yes 	No 	11. Patient Friendly Fast Facts in English and Spanish ** (IRB approval required)

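### The response comparison rests on a logistic model too rich for the likely number of responders, with an undefined failure trigger and a fallback that drops K-RAS and gives no between-arm effect estimate

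*Combined protocol and SAP*

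**What the plan says.** Tumour response is a secondary objective (Section 3.0). Section 10.0 contrasts the arms with a "logistic regression model adjusted for age, sex, race and the baseline tumor K-RAS status (mutated, wild type"), and promises the odds ratio, its 95% confidence interval and a p-value. The switch follows: "If the logistic model fails due to small cell counts then treatments will be contrasted with regard to response using" Fisher's Exact Test. The Synopsis has the same wording.

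Other text that bears on this:

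- In Section 10.0 the response contrast stands under the OS and mPFS-2 bullets; in the Synopsis it stands under mPFS-2 only. The response-rate bullet itself plans proportions with a 95% confidence interval.
- Section 5.0 stratifies randomisation by KRAS status.
- The accrual table in Section 9.0 projects race by sex. The row "Black or African American" has 3% male and 3% female, Asian 2% and 2%, White 45% and 45%.
- The documents do not give an expected response rate, a coding for race, a definition of model failure, or an effect estimate to go with Fisher's test.

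**The concern.** A maximum-likelihood logistic model needs enough responders, spread over the covariate levels. With race at three levels, this one has six coefficients besides the intercept: treatment, age, sex, two for race, and K-RAS. A race level with no responder sends its own coefficient to minus infinity, yet software will usually still print a treatment odds ratio. One analyst could call that a failure and move to Fisher's test; another could report the odds ratio. The plan supports either reading, and the decision falls when the outcome data are in hand.

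At stake is which p-value is reported for a stated secondary objective, and whether any between-arm effect size comes with it.

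**Working it through.** **1. The plan's sample size.** It states that "36 subjects per group are necessary to obtain 80% power" and that "With 5% lost to follow-up the sample size required per group is 38". The medians are 1.9 and 3.8 months, so the hazard ratio is 0.5 if survival is exponential. No alpha is stated for this calculation; two-sided 0.05 is assumed.

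- Freedman events: (1.96 + 0.842)² × (1.5/0.5)² = 7.85 × 9 = 70.6, so 71.
- Mean event probability over 36 + 12 months: 0.991.
- Per group: 71 / 0.991 / 2 = 35.8, so 36; then 36/0.95 = 37.9, so 38. Total 76.

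The plan's figure reproduces, and 76 is the number available to the response model.

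**2. Race cells** (Section 9.0). Black: 76 × 6% = 4.56, about 5. Asian: 76 × 4% = 3.04, about 3. White: 76 × 90% = 68.4.

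**3. Expected responders.** The rate p is an assumption. 76 × 5% = 3.8; 76 × 10% = 7.6; 76 × 20% = 15.2.

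**4. Empty race level and empty arm**, taking p equal in all groups:

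- At least one minority level with no responder: 1 − [1 − (1−p)⁵][1 − (1−p)³]. At 5%: 1 − 0.226 × 0.143 = 96.8%.
- At least one arm with no responder: 1 − [1 − (1−p)³⁸]². At 5%: 1 − (1 − 0.142)² = 26%.
- If race is coded White/non-White, no responder among the 8 non-White patients: (1−p)⁸.

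| Response rate | Empty race level (3 levels) | No non-White responder | Empty arm |
|---|---|---|---|
| 2% | 99.4% | 85% | 71% |
| 5% | 96.8% | 66% | 26% |
| 10% | 88.9% | 43% | 4% |
| 20% | 67.2% | 17% | <0.1% |

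**5. Is the treatment odds ratio still finite?** Trials were simulated with 38 per arm, the Section 9.0 race mix, and covariates unrelated to response, and checked for separation by linear programming. K-RAS was taken as 45 or 50% mutated (an assumption).

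| Rate, both arms | All coefficients finite | Treatment odds ratio finite | Same, race dropped |
|---|---|---|---|
| 5% | about 3% | about 73% | about 74% |
| 10% | about 10% | about 95% | about 95% |

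When both arms had responders, the treatment odds ratio was finite in 96% of trials at 5 v 5% and 99% at 10 v 10%. It is lost mainly through an empty arm, not through race.

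**6. Does the choice of test matter?** The unclear case is the one where both arms have responders but a race level has none. The simulation used 1,500 trials per setting, with K-RAS 45% mutated and 50% male assumed, and a likelihood-ratio test from the logistic model.

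| RGF v VOR/HCQ | Trials in the unclear case | Logistic p<0.05 | Fisher p<0.05 | Tests disagree |
|---|---|---|---|---|
| 2 v 10% | 50% | 15% | 2% | 13% |
| 5 v 15% | 75% | 24% | 9% | 14% |

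The last three columns are shares of the trials in the unclear case. A separate simulation gave the same 50% and 75%, with disagreement in 11 to 13%. Over all trials in these settings, the conclusion would turn on the choice in between 0.50 × 0.11 = 5.5% and 0.75 × 0.14 = 10.5%.

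**The case against.** The strongest reply is that the plan promises one effect estimate, the treatment odds ratio, and this usually survives. An empty race level makes only that level's coefficient infinite; its patients stop contributing and the treatment odds ratio remains a valid finite estimate. A reader might infer from the race counts that the planned model will almost never deliver its result. The documents do not support that: the inference counts a trial as lost when any coefficient is infinite, and it needs a low response rate and a race coding that the plan does not state. This objection stands.

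Removing covariates also does little by itself. With treatment and K-RAS only, the odds ratio is finite in 75% of trials at 5 v 5% and 97% at 10 v 10%, against 72% and 96% for the full model in the same runs. That stands too: the gain must come from a method that still gives an interval when one arm is empty.

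Two further inferences go too far. A reader might say that the fallback is picked after the fact, but it is named in advance and only its trigger is open. A reader might say that the fallback leaves a p-value and nothing else, but response proportions with a 95% confidence interval are planned whichever test is used. What is missing is a between-arm estimate.

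Finally, age, sex, race and K-RAS are also used in the PFS-1 model. Consistency is a fair reason there, where nearly every patient is expected to have an event, but it does not carry over to 4 to 8 responders.

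**Conclusion.** The point holds in a limited form. The model is too rich for the likely number of responders, and its failure is undefined in a situation that arose in at least half of the simulated trials at 2 v 10% and 5 v 15%. In those trials the two candidate tests disagree at 0.05 in about 11 to 14%. The fallback ignores the stratification factor and has no between-arm odds ratio or interval.

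This rests on assumptions that the documents neither confirm nor exclude:

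- **Response rate.** None is stated. The only colorectal activity that Section 2.4.1 reports from phase I is prolonged stable disease in two patients, which is consistent with low rates. At 20% an empty race level still occurs in about 67% of trials, but an empty arm almost never does.
- **Race.** Section 9.0 is a projection, and separate race levels are assumed. White/non-White coding lessens the problem without removing it.
- **Test.** The disagreement figures use a likelihood-ratio test. The plan does not say which test gives the p-value, and another could change the share.
- **Numbers.** Patients off study before completing cycle 1 are not evaluable for efficacy, so the cells could be smaller than shown.

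The endpoint is secondary and does not size the trial.

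**What to change.** Replace the model and its fallback by one pre-specified analysis. Either of these would do:

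- Firth-penalised logistic regression with treatment and K-RAS, with a profile penalised-likelihood 95% confidence interval and p-value. It gives a finite estimate when one arm has no responders.
- An exact conditional odds ratio for treatment stratified by K-RAS, with exact 95% confidence interval and p-value. It gives a one-sided bound when one arm has no responders.

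State that if neither arm has a responder, only the proportions with exact confidence intervals are reported. Move the text to the response-rate bullet. Apply the same rule to the response contrast in the crossover population under mPFS-2, which is a smaller group with sparser cells.

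The cost is SAP wording. Adjustment for age, sex and race is given up, which 4 to 8 responders could not support in any case. The exact version is somewhat conservative.
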